4.0 Study Endpoints

The outcome measures have been chosen to provide the most complete and accurate evaluation of therapy results. Outcome measures are numerous in the voice field, and to allow comparison across studies, the American Speech-Language-Hearing Association (ASHA) has recently developed a recommended protocol for instrumental assessment of voice(36). We modeled our measurement methods on these recommendations and added supplementary outcomes relevant to this study.

Voice measures. [Note: voice measurements will be obtained from the participants' standard of care voice assessments]

Videostroboscopy: Recordings of vocal fold vibration from sustained phonations of /i/ at various pitch and loudness levels will be used 1) to assess the parameters described in the Voice-Vibratory Assessment with Laryngeal Imaging (VALI) rating form(37), and 2) for measurements of normalized glottal gap (NGG)(38).

Acoustic measures: The Computerized Speech Lab (CSL) is used to record sustained phonation at various pitch and intensity levels, reading of the Consensus Auditory-Perceptual Evaluation of Voice (CAPE-V)(40) sentences, as well as a short natural conversation with the SLP. Acoustic analysis will include: 1) measures of voice intensity: habitual and maximum sound pressure levels (SPL); 2) measures of fundamental

frequency (F0): mean, minimum, and maximum vocal F0, and 3) measures of voice quality: cepstral peak, jitter, shimmer, and harmonics-to-noise ratio.

Perceptual judgments of voice quality: The CAPE-V(40) rating form will be used for the judgment of voice quality of sustained phonation, reading and conversational speech tasks recorded via CSL. The CAPE-V form includes ratings of overall severity, roughness, breathiness, strain, pitch, and loudness, as well as qualitative information about resonance and additional features.

Patient self-assessments: Patients are asked to complete the 1) Voice Handicap Index (VHI): a questionnaire that evaluates the degree of handicap experienced by the patient in relation to their voice use(41); 2) the GFI(42): a validated disease-specific impairment instrument conceived to assess symptoms related to glottal insufficiency; 3) the RSI(43), a validated self-administered questionnaire to assess symptoms related to LPR; and 4) the Communicative Participation Item Bank (CPIB) general short form(44). Patients are also asked to rate their perceived phonatory effort (PPE) on a direct magnitude estimation scale(45) following the speaking and voicing tasks recorded with the CSL.

Aerodynamic measures: The Phonatory Aerodynamic System (PAS) is used to measure 1) mean glottal airflow rate: estimated from sustained phonation of a vowel(36); 2) average subglottal air pressure (P_s): measured during the production of a voiceless plosive consonant (/p/) at normal pitch and loudness, an accepted indirect and non-invasive measurement method for P_s (46); and 3) laryngeal resistance: calculated by dividing subglottal pressure by mean glottal airflow.

Phonation duration (MPT): The maximum phonation duration of the vowel /a/ is measured via CSL.

Respiratory measures (respiratory measures will be recorded solely as part of the study).

Spirometry: Spirometry will be used to measure 1) forced vital capacity (FVC), 2) forced expiratory volume in one second (FEV1), and calculate the 3) FEV1/FVC ratio. The predicted values (%) of these three measures will also be reported. The patient will be asked to take a full inspiration, blow out the air forcefully and then exhale slowly to residual volume in the spirometer. The task is repeated at least three times, until the two best measurements differ by no more than 0.15.

Muscle pressure measures: 1) MIP: measured at functional residual capacity, is an indicator of inspiratory muscle strength. Patients will be instructed to exhale fully and then inhale with maximal effort with lips sealed to the pressure meter for at least 2 seconds. 2) MEP: measured at full lung capacity, is an indicator of expiratory muscle strength. Participants will be instructed to take a full breath and then exhale with maximal force with lips sealed to the pressure meter for at least 2 seconds.

5.0 Inclusion and Exclusion Criteria/ Study Population

Patients who are diagnosed with presbyphonia and who have already sought and begun voice care at MUSC, will undergo a brief screening interview by [name], after which qualifying patients will be offered participation in the study. A study team member will meet with interested participants and will provide a thorough description of the study prior to obtaining formal written consent. Participants who don't meet stratification requirements will be excluded from the study.

Inclusion Criteria

The participant:

- must receive a diagnosis of presbyphonia by a trained laryngologist. The
 diagnosis will be given following a visual examination of the larynx if the
 observations are consistent with the characteristics of a presbylarynx, as
 judged by the laryngologist.
- must have already undertaken their voice care at MUSC
- must be 50 years and older
- must be English-speaking
- must sign the informed consent

Exclusion Criteria

The participant

- has received voice therapy in the past year (other than current care)
- presents with a vocal fold pathology other than presbyphonia
- has a known neurologic or a progressive neuromuscular disease
- doesn't meet the stratification requirements for muscle pressure
- has a medical condition that could be aggravated by the experimental intervention, or any condition judged by the physician ([name]) as being unsuitable for respiratory training.
- has dysarthria or a language disorder
- has a hearing loss that is not adequately managed
- has a cognitive disorder that might affect treatment compliance
- is unable to give informed consent

Inclusion of Women

No subjects will be excluded based on gender. Based on published literature, treatment seeking patients with presbyphonia are generally equally divided between female and male. Thus, we estimate that approximately 50% of study participants will be female. No outreach program to recruit women is planned, because all patients with presbyphonia who meet inclusion criteria after undergoing a voice evaluation at the participating institution, regardless of gender, will be invited to participate. While no subjects will be excluded based on gender, it is highly likely that the majority of participant raters will be women as that is the current composition of speech-language pathologists.

Inclusion of Minorities

No subjects (patient or control subject groups) will be excluded based on race or ethnic origin. However, only English-speaking participants will be included in the study.

Gender, ethnic and racial information will be collected at the study enrollment. Ethnicity (i.e., Hispanic/Latino, Non-Hispanic/Latino) will be recorded separately from race. All applicable racial categories (i.e., American Indian/Alaskan Native, Asian, Native Hawaiian or other Pacific Islander, Black/African American, White) are recorded for each subject. All ethnic and racial totals will be reported, including specific categories for those individuals who report mixed racial descent. The Targeted/Planned Enrollment Tables for the participating institution are included in the Targeted/Planned Enrollment section, which indicate the anticipated ethnic and racial mixes of the subject sample. Numbers reflected in these tables parallel the ethnic and racial mixes of the service areas of the participating institution. No outreach program to recruit minorities is planned because all patients with presbyphonia who meet inclusion criteria after undergoing a voice evaluation at the participating institution, regardless of race or ethnic origin, will be invited to participate.

While no subjects will be excluded based on race/ethnicity, it is highly likely that all of the participant raters will be White Non-Hispanic as that is the current composition of speech-language pathologists.

Inclusion of Children

It has been well documented that infants and children differ significantly from adults in laryngeal, respiratory and neurological anatomy and physiology. Presbyphonia is a voice disorder caused by agerelated changes in the laryngeal, respiratory and neurological systems, including muscle atrophy, changes in the vocal fold histology and in lung tissue and ribcage mobility. The aging process may differ between individuals, with symptoms of presbyphonia reported to occur as early as 50 years old. No case of presbyphonia has ever been reported in a child under 18 years old. The aim of this study is to assess the effects of respiratory training in patients with presbyphonia, therefore, the topic is not relevant to children. Although respiratory training could potentially be beneficial for treating other types of voice disorders, including those affecting children, a separate, age-specific study in children, would be warranted. Therefore, children are not a part of the current study.

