There are two main types of respiratory training: inspiratory training, also called inspiratory muscle strength training (IMST), and expiratory training, also called expiratory muscle strength training (EMST). In this application, we propose a novel, proof-of-concept study to test whether the addition of either type of respiratory training to the standard of care voice therapy (voice exercises) enhances respiratory and voice outcomes. This study will permit, for the first time, the comparison between inspiratory and expiratory training. The theoretical framework is: inspiratory training strengthens the inspiratory muscles and thus increases both vital capacity and the ability to counteract passive recoil of the lungs, improving

the quantity of and control over the airflow available to drive the vocal folds. Expiratory training strengthens the expiratory muscles to expand the expiratory reserve volume and provide more airflow for voicing. Using pulmonary function tests and respiratory pressure measures, combined with voice assessments, we will specifically evaluate our hypotheses and determine the independent effects of inspiratory training and expiratory training on respiratory function and voice production. We will also evaluate the interaction between the type of respiratory training and a patient's baseline respiratory function. This will provide mechanistic information to guide the future selection of the type of respiratory training to augment voice therapy, to promote an impairment-specific intervention paradigm.

Forty-eight participants diagnosed with presbyphonia will be included in the study and will be stratified and blocked-randomized into one of the three intervention groups (two experimental groups and one control group), using a 3-parallel arm design: 1) inspiratory training (IMST) (experimental group), 2) expiratory training (EMST) (experimental group), or 3) voice exercises (VFE) (control group), delivered four times during a 60-minute therapy session. Monitored home practice will consist of 10 minutes of twice daily exercise for the duration of therapy. Participants from all three groups will carry on with their standard of care voice therapy with a certified SLP.

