3.0 Intervention to be studied

Participants in all groups will have already undertaken their voice care (voice assessments and voice therapy with a certified SLP) at MUSC. Depending on their group assignment, participants will also receive either inspiratory training, expiratory training, or no respiratory intervention (standard of care group). The experimental and standard of care interventions are described below.

Inspiratory Training [Experimental intervention]: Inspiratory training will be conducted using an inspiratory pressure threshold trainer (Philips Respironics® Threshold IMT or POWERbreathe® Medic Plus, for patients with a MIP of 55 cmH₂0 and over), which consists of a mouthpiece with a spring-loaded valve(13, 25). The valve blocks the airflow until the threshold pressure is achieved and allows airflow as long as the sufficient pressure is maintained. The threshold will be set at 75% of the participant's initial MIP, as reported in the literature with elderly participants(16). If it is too hard for the participant, the load will be lowered until the participant is able to perform the exercises. The load will be adjusted weekly by the study team member to maintain a threshold at 75% of the participant's MIP. Daily practices will consist of 5 sets of 5 breaths with the device with a break between sets, repeated twice daily (15, 18, 31).

Expiratory Training [Experimental intervention]: Expiratory training will be conducted using an expiratory pressure threshold trainer (EMST150TM) which consists of a mouthpiece with a spring-loaded valve. The valve blocks the airflow until the threshold pressure is produced (set at 75% of the participant's initial MEP, per literature with similar age groups(32-34)), and allows the airflow as long as the sufficient pressure is maintained. Participants will be asked to exhale forcefully into the mouthpiece after a full inspiration. If it is too hard for the participant, the load will be lowered until the participant is able to perform the exercises. The load will be adjusted weekly by the study team member to maintain a threshold at 75% of the participant's MEP. Daily practices will consist of 5 sets of 5 breaths with the device with a break between sets, repeated twice daily(32-34).

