8.0 Recruitment Methods

Following IRB approval, participants will be recruited from the treatment-seeking population at the Evelyn Trammell Institute for Voice and Swallowing (division of the Department of Otolaryngology-Head & Neck Surgery) - Medical University of South Carolina (MUSC). As part of usual care, all patients will undergo a videostroboscopic assessment conducted by the laryngologist, [name] and will be referred to voice

therapy with a certified SLP to start usual treatment. Patients will undergo a brief screening interview by [name], after which qualifying patients will be offered participation in the study.

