10.0 Study Design / Methods

Overview

After being enrolled in the study, treatment-seeking patients with a diagnosis of presbyphonia will undergo baseline respiratory assessments including spirometry and respiratory muscle strength measures as well as voice recordings (acoustic assessments). Participants will then be blocked-randomized (based on their MIP and MEP) to one of three groups using a 3-parallel arm design: (2 experimental groups and 1 control group), using a 3-parallel arm design: 1) inspiratory training (IMST) (experimental group), 2) expiratory training (EMST) (experimental group), or 3) standard of care (VFE) (control group), delivered four times (see table 1 for participant timeline). The sessions will occur on the same days as the participants' scheduled voice therapy sessions when possible. Participants will be asked to practice their respective exercises for 10 minutes, twice daily, seven days a week during the duration of the study. A final assessment session, after the 4th therapy session, will mirror the baseline measures. Participants will receive a monetary compensation of \$20 for each study visit, for a maximum of \$80 for the whole study. Payments will be made via cash. Outcomes that rely on subjective judgment (visual ratings of

videostroboscopy and perceptual judgments of voice quality) will be rated by trained judges (SLPs) blinded to the group assignment. [**Note**: Long-term follow-up will not be conducted. This study's focus is on the mechanistic effects of the intervention; future studies, given positive outcomes from this study, will explore the effectiveness and long-term effects.]

Table 1: Participant Timeline

Visit 1	Visit 2	Visit 3	Visit 4
Baseline assessment session			
Therapy session 1	Therapy session 2	Therapy session 3	Therapy session 4
			Final assessment session

Patient Participants

Standard of Care Assessments (Procedures being performed already for diagnostic purposes)

- Laryngeal imaging: prior to the examination, the laryngologist will administer topical lidocaine and neosynepherine in a spray to one of the nasal cavities. The laryngologist then passes the camera through the nose to examine the vocal folds. The participant will be asked to sustain phonation on the vowel /i/ for at least 3 seconds and to repeat with pitch and loudness variations.

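### Patients may enter after an unlimited amount of current voice therapy, so within-arm change and the Aim 2 responder classes partly reflect when they enrolled

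*Combined protocol and SAP*

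**What the plan says.** Several sections bear on when a patient enters relative to the start of voice therapy.

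- **Section 3.0:** "Participants in all groups will have already undertaken their voice care (voice assessments and voice therapy with a certified SLP) at MUSC".
- **Section 5.0, inclusion:** the participant "must have already undertaken their voice care at MUSC". The opening paragraph also describes patients whose voice care has begun.
- **Section 5.0, exclusion:** the participant "has received voice therapy in the past year (other than current care"). No maximum number of sessions or weeks is given for the exempted care.
- **Section 8.0:** after stroboscopy, patients are referred to "therapy with a certified SLP to start usual treatment", and the screening interview is described next. Section 9.0 seeks the consent meeting on the same day if possible.
- **Section 10.0, Overview:** "The sessions will occur on the same days as the participants' scheduled voice therapy sessions when possible". Table 1 puts baseline and study session 1 at Visit 1. For the end of the study: "A final assessment session, after the 4th therapy session, will mirror the baseline measures".
- **Section 1.0:** "Participants from all three groups will carry on with their standard of care voice therapy with a certified SLP".

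The two Aim 2 outcomes sit in different places. In section 10.0 the GFI appears only among standard-of-care procedures done for diagnosis. The maximal sustained vowel that yields MPT appears only in the study's own acoustic assessment. Section 4.0, however, says voice measures come from the standard-of-care assessments, so even the MPT source is not fully clear.

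Randomisation is stratified on maximum inspiratory and expiratory pressure (MIP, MEP) only. The Aim 1 model has time and intervention. Neither it nor the Aim 2 predictor list contains prior therapy.

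**The concern.** A one-year exclusion for voice therapy keeps out patients whose voice has recently been changed by therapy. Exempting the current course removes that protection for the therapy closest to baseline, and section 3.0 goes further by requiring that such therapy has already taken place. A patient treated elsewhere 11 months ago is excluded. One several sessions into the current course is eligible.

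Two things are at stake. First, the pre-post change in each arm covers a different stretch of the therapy course for different patients. The plan relies on this change: the Sample Size Justification sets d=0.90 for within-subject as well as between-subject differences. Second, Aim 2 classes patients as improved after inspiratory or after expiratory training by an MPT rise of at least 4 s or a GFI fall of at least 4 points. That is a within-arm classification with no randomised contrast to absorb differences in timing. If the GFI baseline is the diagnostic assessment and the MPT baseline is Visit 1, GFI gain made on VFE before randomisation counts as response to respiratory training, while MPT gain made before Visit 1 is lost.

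**Working it through.** **1. Can baseline follow therapy?** Sections 3.0 and 5.0, read together, require therapy to have begun. Section 8.0, section 9.0 and Table 1 fit entry near referral. Table 1 does not settle it: it orders baseline before *study* session 1, and study sessions are run by a study team member and share days with SLP sessions only when possible. Nothing ties study session 1 to the first SLP session. Baseline can therefore fall before therapy or well into it.

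**2. The plan's own figure.** Inputs from the Sample Size Justification: d=0.90, alpha 0.1 (taken as two-sided), power 80%, 15 per group. By the normal approximation, n = 2(1.645 + 0.842)²/0.90² = 15.3, which rounds up to 16 and is close to the stated 15. Power at 15 per group is Φ(0.90 × √(15/2) − 1.645) = Φ(0.820) = 79%. The figure reproduces and serves as the reference for step 3.

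**3. Effect on the randomised comparison.** Assignment follows baseline, so prior sessions are balanced in expectation. What remains is noise. The documents give neither the VFE gain nor the spread of prior sessions. Assumptions: a four-session course, a linear total MPT gain of 2 to 4 s (0.5 to 1.0 s per session), and prior sessions spread evenly over 0 to 4.

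- SD of {0, 1, 2, 3, 4} = 1.41 sessions, or 0.7 to 1.4 s.
- Chance imbalance between two arms of 16: standard error 1.41 × √(2/16) = 0.50 sessions, or 0.25 to 0.5 s.
- Taking the plan's MPT SD of 5.1 s as the SD of change, total SD becomes √(5.1² + 0.7²) = 5.15 s to √(5.1² + 1.4²) = 5.29 s, an increase of 1% to 4%.
- At the upper end d falls to 0.90 × 5.1/5.29 = 0.867, and power to Φ(0.867 × √7.5 − 1.645) = 77%.

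Larger losses need implausible inputs. An added SD of half or three-quarters of the planned SD would cut power to 71% or 63%. Those are 2.55 s and 3.83 s, whereas a gain bounded between 0 and 4 s cannot have an SD above 2 s.

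**4. Effect on Aim 2, MPT rule.** Let G be the total VFE gain and f the fraction made before baseline. With SD of change 5.1 s, the share reaching 4 s from VFE alone is 1 − Φ((4 − G(1 − f))/5.1).

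| Assumed G | f = 0 | f = 0.5 | f = 1 |
|---|---|---|---|
| 2 s | 35% | 28% | 22% |
| 3 s | 42% | 31% | 22% |
| 4 s | 50% | 35% | 22% |
| 5 s | 58% | 38% | 22% |

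**5. Effect on Aim 2, GFI rule.** Take a patient whose whole VFE gain precedes Visit 1. Assume that gain is 4 GFI points and the SD of change is the plan's 4.5. From a diagnostic baseline, the chance of a 4-point fall is 1 − Φ((4 − 4)/4.5) = 50%. From a Visit 1 baseline it is 1 − Φ(4/4.5) = 19%. So for one entry time, with G = 4 s, the chance is 22% on MPT and 50% on GFI, with no effect of respiratory training in either figure.

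**The case against.** Most of the recruitment text points to early entry. Patients are invited after a voice evaluation, referral to start treatment is described before screening, consent is sought the same day if possible, and section 10.0 says research visits fall on speech therapy days. Only the parenthesis in section 3.0 says outright that therapy itself has been undertaken; voice care in section 5.0 could mean assessment alone. The trial also asks an add-on question in a pilot, which patients already in care can answer. All of this makes late entry less likely in practice. It does not remove the conflict, because the eligibility text admits late entry without limit.

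A reader might infer more than the documents support:

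- **That the VFE control course is not a full one.** No section defines a full course. Controls receive four study sessions, twice-daily home practice at four VFE repetitions against two in the training arms, and continuing SLP therapy.
- **That MIP and spirometry baselines are contaminated.** No section says VFE changes them. Section 1.0 says voice exercises target the vocal folds, and the Sample Size Justification treats voice therapy alone as directly addressing only laryngeal deficits.
- **That the arm comparison is biased against controls whose gain is already spent.** That needs a ceiling or an interaction the documents do not describe. With additive effects, gain made before randomisation cancels between arms in expectation.

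The power loss in step 3 is also small. These objections confine the point to within-arm change and Aim 2, where randomisation gives no protection.

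**Conclusion.** The point holds in a limited form. The sections disagree on whether therapy precedes entry, and nothing limits, stratifies on or adjusts for prior sessions. The randomised Aim 1 contrast remains unbiased in expectation, with power falling from about 79% to about 77% at worst under the step 3 assumptions and a chance imbalance of 0.25 to 0.5 s (one standard error).

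Within-arm change and the Aim 2 classes are more exposed. Under the assumptions in steps 4 and 5, entry time alone moves the MPT responder share between 50% and 22%, and the two responder rules can shift apart for the same patient. These sizes rest on assumed VFE gains and on using the plan's SDs of the measures as SDs of change. The different-baseline problem also depends on the GFI baseline being the diagnostic assessment; section 10.0 suggests this, but no section dates it against therapy. This is a cheap improvement worth making, not a flaw that undermines the trial.

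**What to change.** Reconcile sections 3.0, 4.0, 5.0, 8.0 and 10.0 (including Table 1 and the standard-of-care assessment list) so that the Visit 1 baseline is completed before or on the day of the first SLP therapy session of the current course.

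If patients already in therapy are kept:

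- record the number of prior current-course sessions from the chart, which the study already reviews for appointments;
- include that number as a covariate in the Aim 1 and Aim 2 models;
- collect the GFI and the other self-ratings at Visit 1, so that MPT and GFI share one baseline.

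The cost is a wording change and, on the second route, a few short questionnaires at Visit 1. On the first route some patients already in therapy may become ineligible. The documents do not say how many. Projected accrual is 64 for 48 places, but whether that figure already allows for refusals and stratification exclusions is not stated.
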